To address this hypothesis, in the present study we propose to conduct a prospective, randomised controlled study in patients with protective stoma, aiming to investigate whether stimulation of stoma drainage fluid through the anus to an open intestinal segment prior to stoma closure is beneficial for the recovery of bowel function, reduction of complications and improvement of intestinal dysbiosis, and to provide high-level evidence for the clinic.

II. Purpose of the study

To analyse the occurrence of defecation complications, rectal function and quality of life indicators after collecting stoma discharge for anal re-infusion to patients after performing protective ileostomy in anus-preserving surgery for middle and low rectal cancer, so as to evaluate the impact of collecting stoma drainage fluid for anal re-infusion on the recovery of patients' intestinal function.

III. Subject of the study

(i) Inclusion criteria

1. Age: 18~75 years old, male or female;
2. Pathological diagnosis of adenocarcinoma of the rectum on preoperative biopsy;
3. Clinical staging was T1-4aN0-2M0;
4. No distant multiple metastases;
5. ECOG rating 0-2;
6. Cardiac, pulmonary, hepatic and renal functions met the criteria for surgical tolerance
7. Clinical diagnosis of middle and low rectal cancer, the lower edge of the tumour is within 10cm from the anal verge, and it is proposed to perform radical rectal surgery and prophylactic ileostomy at stage I, and intestinal closure at stage II;
8. Patients and their families were able to understand and willing to participate in this clinical study and signed an informed consent form.

(ii) Exclusion criteria

1. Previous history of malignant colorectal tumour or recently diagnosed combination of other malignant tumours;
2. Patients with combined intestinal obstruction, intestinal perforation, intestinal haemorrhage, etc. requiring emergency surgery;
3. Neighbouring organs requiring combined organ removal;
4. ASA classification \geq Grade IV and/or ECOG physical status score > 2 ;
5. Those who have serious liver and kidney dysfunction, cardiopulmonary dysfunction, coagulation dysfunction or combined serious basic diseases cannot tolerate the surgery;
6. Have a history of serious mental illness;
7. Pregnant or breastfeeding women;
8. Those who have a history of taking steroid drugs;

9. Patients with other clinical and laboratory conditions considered by the investigator to be inappropriate for participation in the trial;

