10. One week before the operation, there are signs of infection, body temperature rises $>37.5^{\circ}\text{C}$, blood WBC $>10.0 \times 10^9/\text{L}$;
11. History of antibiotic use 1 week prior to surgery (excluding preoperative shock medication);
12. Preoperative neoadjuvant patients

(iii) Exit criteria

1. Accompanied by other non-oncological conditions that make it impossible for the patient to continue to receive this treatment plan;
2. After enrolment in the study, patients who required emergency surgery due to intestinal obstruction, perforation, or bleeding, et al. prior to stoma closure;
3. Patients with pathologically confirmed distant metastases after rectal surgery, including liver, pelvis, ovary, peritoneum, and distant lymph node metastases;
4. Intraoperative exploration for middle and low rectal cancer in anus-preserving surgery for those who need combined organ resection;
5. After enrolment in the study, patients requested to withdraw from the study cohort for various reasons, or were unable to complete the study programme and follow-up for various reasons;
6. Anastomotic fistula, severe anastomotic stenosis (inability to pass through enteroscopy or oesophageal finger and inability to dilate via oesophageal finger) after radical rectal surgery.

IV. Study endpoints

(i) Primary study endpoints:

Incidence of major LARS after 6 months of stoma closure.

(ii) Secondary research endpoints:

1. Bacteriological sequencing 1 month after stoma closure

[figure not shown]
2. Anorectal function (LARS questionnaire, Wexner¹⁵ incontinence score, MSKCC¹³⁻¹⁴ bowel function questionnaire), Glazer pelvic floor muscle surface electromyography, and quality of life scores after 1 month of stoma return.

3. Recovery of postoperative bowel function

After reversal surgery, time to oral feeding, time to anal defecation after reduction surgery, and rate of intestinal obstruction (intestinal obstruction was defined as ,inability to tolerate food for more than 72 H or the need for re-fasting or gastrointestinal decompression) were observed.

V. Research design

The study was a prospective randomised design with simple randomised grouping, randomised by prior computer-generated random number tables. The expected recruitment cut-off date for all subjects was 1 November 2022, with a predictable sample size of 60 cases to be enrolled based on patient admissions to the hospital. The enrolment process is as follows

(i) Transanal reinfusion of stoma discharge

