IX. Sample size calculation

The sample size was calculated using PASS 15 software, with the major LARS incidence rate at 6 months after stoma closure surgery as the primary outcome. Based on retrospective data from the authors' centre, the major LARS rate at 6 months after stoma closure surgery was estimated to be 14% in the stoma discharge reinfusion group and 47% in the control group. Thus, a sample size of 27 patients was required to achieve 80% power in detecting differences, with a two-sided level of significance of 0.05.

Assuming a dropout rate of up to 10%, 60 patients were enrolled.

X. Methods of statistical analysis

(i) Definition of analysis set

1. Full Analysis Set (FAS)

According to the basic principle of intentional analysis (ITT), all enrolled subjects who were given a randomisation number will be included in the FAS. the FAS is the primary dataset for the evaluation of the efficacy of this study.

2. Compliance with the programme set (Per-Protocol Set, PPS)

PPS is defined as all cases in which planned treatment and visits were completed as specified in the protocol and there were no protocol violations that significantly affected outcomes. Patients with protocol violations that significantly affect the protocol will be excluded from this analysis set. Protocol violations that significantly affect efficacy will be identified at the time of data review. PPS is a secondary data set for the efficacy evaluation of this study.

3. Safety Set (SS)

Cases that completed at least one safety evaluation data after enrolment constituted the safety population of this study. The safety population was the primary population for the safety evaluation of this study.

(ii) Methods of statistical analysis

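### Nothing in the allocation or the primary test limits or adjusts for chance imbalance in tumour height or arm size among 60 patients; the test stays valid, but precision is given away cheaply

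*Combined protocol and SAP*

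**What the plan says.** Inclusion criterion 7 in Section III admits middle and low tumours together: "the lower edge of the tumour is within 10cm from the anal verge". Section II describes the setting as "protective ileostomy in anus-preserving surgery for middle and low rectal cancer". Neither section gives a distance that separates low from middle.

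Section V specifies "simple randomised grouping, randomised by prior computer-generated random number tables" and a target of 60. No blocks, strata or minimisation appear anywhere.

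The primary endpoint in Section IV is "Incidence of major LARS after 6 months of stoma closure". Section X (ii), item 2, compares it between arms with a chi-square test and names no covariate or stratum.

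Tumour height is not named among the baseline variables in Section VII, item 1. It may be captured under imaging there, or under the oncology data mentioned in Section VIII (ii), but the plan does not say so.

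**The concern.** The primary outcome is bowel function after a resection that keeps the anus. It is plausible that a lower tumour leaves less rectum and worse function. If so, height is prognostic, and a chance excess of low tumours in one arm moves the observed difference in major LARS. With simple allocation of 60 patients, sizeable gaps are not rare, and the planned analysis would not correct them. As the baseline list stands, a gap might not even be reported. A reader of the result could then offer height as a rival explanation. Simple allocation also leaves the arm sizes to chance.

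**Working it through.** **Inputs from the plan (Section IX).** Assumed major LARS rates of 14% with reinfusion and 47% without; a two-sided test at the 5% level; for the size, "a sample size of 27 patients was required to achieve 80% power in detecting differences"; and an allowance of 10% for dropout, which brings the total to 60.

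**Assumptions, not in the documents.** Share of low tumours, q: 30% to 50%. Excess risk of major LARS in low over middle tumours, d: 20 to 40 points.

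**1. The plan's own figure.** With unpooled variance, n = (1.960 + 0.842)² × (0.14×0.86 + 0.47×0.53) / 0.33² = 7.85 × 0.3695 / 0.1089 = 26.6, so 27. Read as per arm, 54 / 0.9 = 60. The figure reproduces.

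**2. Height imbalance under simple allocation.** The SD of the between-arm difference in the share of low tumours is about √(4q(1−q)/N). For N = 60 this is √(4×0.25/60) = 12.9 points at q = 50% and √(4×0.21/60) = 11.8 points at q = 30%. Simulated frequencies, with the number of low tumours left random:

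| N | q | gap ≥ 15 points | gap ≥ 20 points |
|---|---|---|---|
| 60 | 30% | 21% | 9.8% |
| 60 | 50% | 25% | 13.0% |
| 54 (after dropout) | 30% | 23% | 11.4% |
| 54 (after dropout) | 50% | 27% | 14.3% |

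If exactly 18 or exactly 30 of the 60 tumours are low, the exact chance of a gap of at least 20 points is 10.0% or 15.5%.

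**3. Shift in the primary difference** = gap × d. A 20-point gap gives 0.20×20 = 4 to 0.20×40 = 8 points. A typical (one-SD, 13-point) gap gives 2.6 to 5.2 points.

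**4. Ordinary sampling error, 30 per arm, no treatment effect.** √(2×0.47×0.53/30) = 12.9 points if both arms are at 47%. √(2×0.305×0.695/30) = 11.9 points if both are at the mean planned rate of 30.5%. At the planned rates it is √(0.3695/30) = 11.1 points.

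**5. Validity.** In 40,000 simulated trials with no treatment effect, the unadjusted test rejects in 5.1-5.3%. Among those trials with a gap of at least 20 points, it rejects in 6%, 8% and 10% for d = 20, 30 and 40.

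**6. Power at N = 60**, with q = 50% and the same relative risk (14/47) in both strata:

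| d | simple, chi-square | simple, Cochran-Mantel-Haenszel | stratified, Cochran-Mantel-Haenszel |
|---|---|---|---|
| 20 | 0.813 | 0.811 | 0.829 |
| 30 | 0.811 | 0.821 | 0.837 |
| 40 | 0.814 | 0.840 | 0.851 |

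The analysis change alone therefore gains −0.2, +1.0 and +2.5 points; stratified allocation adds a further 1.2 to 1.8. The gain depends on how the effect acts across heights. With the same odds ratio in both strata, 200,000 simulated trials give gains of about 0 to 3.5 points from the analysis change. With the same 33-point absolute reduction in both strata and q = 30%, they give about 1, 4 and 7 points. With q = 50% that last model cannot hold at d = 30 or 40, because the middle-tumour control rate (32% or 27%) is below 33%.

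**7. Arm sizes.** For a Binomial(60, 0.5) count, a split of 25/35 or worse has probability 24.5%, and one arm starts below 27 with probability 37%. The power cost is small: exact chi-square power is 0.817 at 30/30 and 0.80 to 0.81 at 24/36.

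**The case against.** The strongest reply is that nothing here is an error. Simple randomisation is valid, the chi-square standard error already allows for chance imbalance on every covariate, and the same remark could be made of any small unstratified trial. All of this stands. A reader might infer that the comparison is biased or the test invalid; step 5 shows that it is not. The higher rejection rates there apply only to trials already selected for a large imbalance.

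The second reply is that the documents never say height predicts LARS, give no rates by height and set no cut-point. This also stands: the shift and most of the power gain rest on assumption. The arm-size point does not.

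The third reply is that the gain is small. With half the tumours low and a mean rate of 47%, height explains d²q(1−q)/(p(1−p)) of the outcome variance: 0.04×0.25/0.2491 = 4% at d = 20 and 0.16×0.25/0.2491 = 16% at d = 40. The standard error falls by only about 2% to 8%. It would be wrong to say that stratifying removes most of the noise; it removes most of the part due to height.

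Two further readings go too far. The criterion has no lower limit in centimetres, but surgery that preserves the anus will in practice exclude some of the lowest tumours, so the trial does not span every height from zero. Nor is height certain to be on record: criterion 7 needs only a judgement that the tumour lies within the limit.

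Finally, Section V gives a recruitment cut-off of 1 November 2022 and Section IX speaks of enrolment in the past tense, so a new allocation list may come too late. The analysis change does not depend on it.

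**Conclusion.** The point holds as a cheap improvement, not as a defect that threatens the result. Neither design nor analysis limits or adjusts for imbalance in tumour height, and a 20-point gap has roughly a one in ten to one in seven chance. Its effect, 4-8 points under the assumed range, is well below both the planned 33 points and one standard error. It could not by itself produce the planned effect, and it matters mainly if the true effect is smaller than planned. The size of the shift rests on two assumptions outside the documents: the share of low tumours and their excess risk. Uneven arms need neither assumption, but cost little power.

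**What to change.** Add tumour height, in centimetres from the anal verge, as a named baseline variable in Section VII. In Section X (ii), make the primary test a Cochran-Mantel-Haenszel comparison of major LARS in two height strata, with the cut-point written down before any outcome data are seen. Keep the unadjusted chi-square as a supporting result.

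If allocation has not started, also replace simple randomisation in Section V with computer-generated permuted blocks of varying size, stratified by the same height categories. This controls arm sizes as well.

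The sample size does not change. The analysis change costs one data field and a sentence in the plan. If height turns out to be unrelated to major LARS, adjusting under simple allocation loses about 1 point of power (0.815 to 0.805 in the simulation with d = 0). Blocks make allocation slightly more predictable in an open trial at what reads as one hospital; varying the block size limits that. If the list is already in use, make only the recording and analysis changes.

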Experimental group:

Starting from 1 month after radical rectal surgery, the infusion is performed once a week for 2 months. Each infusion was performed with a liquid diet on the day before, and 400-600 mL of stoma discharge was collected on the same day (if the stoma fluid was limited, it could be blended with warm water), and the reinfusion was performed from the patient's anus using an enema bag, with a flow rate of about 100 mL/min being controlled.

Control group:

No special treatment.

(ii) Preoperative preparation for protective stoma reduction

Stoma closure was performed 3 months after surgery. All patients were reviewed in an outpatient clinic at least 7 days before preparation for stoma closure.

The surgeon is responsible for performing rectal palpation and Lower gastrointestinal tract imaging to rule out anastomotic leakage and anastomotic stenosis.

(iii) Pelvic floor muscle function assessment

Pelvic floor muscle function tests were performed "prior to radical rectal surgery", "prior to stoma closure surgery", "1 month after stoma closure surgery", "3 months after stoma closure surgery" and "6 months after stoma closure surgery" to compare the recovery of pelvic floor muscle function.

(iv) Sequencing of intestinal flora

faecal sampling

Gut microbiological samples were collected using the rectal swab method. Firstly, the perianal area was cleaned using soap, water and 70% alcohol respectively, then a sterile swab was inserted into the anus 4-5cm at the anal sphincter after moistening with saline and gently rotated to take a sample at the anal crypt (traces of faeces were clearly visible on the swab), then inserted into a sterile freezing tube (or the head of the swabs was clipped and dropped into a sterile freezing tube, 3-5 swabs were provided for each sample) and placed in a box containing ice/ dry ice in a foam box,

transported to the laboratory within 24h and stored in a -80°C refrigerator.

Sample delivery

- A. DNA: total amount >500ng, concentration >20ng/ul, no significant degradation, 2g of faecal or intestinal contents;
- B. The sample volume of a single delivery should be ≥ 20 samples, the delivery tube (freezing tube) must be clearly labelled with the sample number, the mouth of the tube should be sealed with Parafilm sealing film (to prevent cross contamination between samples), and the completed delivery order should be sealed in a self-sealing bag and sent to the laboratory with the samples transported on dry ice.

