1. General principles: All statistical tests will be two-sided, and $P < 0.05$ will be considered statistically significant for the differences tested. The description of quantitative indicators will calculate the mean, standard deviation, median, minimum value, maximum value, if it meets the normal variance chi-square, expressed as the mean \pm standard deviation, and use the t-test to compare the differences between the two groups; data that do not meet the normal variance chi-square are expressed as the median (quartile), and the rank sum test is used for comparison. Categorical indicators were described by the number of cases and percentages in each category, and the chi-square test was used to compare the differences between the experimental and control groups.

2. The main outcome indicators of the occurrence of LARS at 6 months after the

reduction were expressed as the number of cases (percentage), and the chi-square test was used to compare the differences between the experimental group and the control group.

Secondary outcome indicator colony species results will be tabulated based on the top 15 species in abundance using cumulative histograms to compare species composition differences between samples. Based on the species abundance information of each sample at the genus level, the top 50 genera of abundance will be selected, and the samples and species will be clustered based on the abundance information of each sample, and heat maps will be drawn. And Shannon diversity index, Simpson index and Chao1 richness index were calculated for Alpha diversity analysis Comparative analysis of microbial community composition of samples between different groups was performed using Beta diversity analysis.

Secondary outcome indicators Wexner score, MSKCC Bowel Function Questionnaire, and QLQ-C30 Quality of Life Scale scores were analysed for repeated-measures data between the two groups, Mauchly's test of sphericity was performed, and ordinary one-way ANOVA or multifactorial ANOVA was performed according to the test results.

x. schedule of visits

| | | | | | | |
|---------------------------------------|--------------------------------------|-------------------|-------------------------------------|--------------------------------------|---------------------------------------|---------------------------------------|

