| sports event | Pre-radi cal rectal surgery | pre-discha rge | Pre-sto ma closure surgery | Post-sto ma closure 1 month | Post-sto ma closure 3 months | Post-sto ma closure 6 months |
| Demographic information | ✓ | | | | | |
| Baseline assessment | ✓ | | | | | |
| bacterial colony sequencing | ✓ | | ✓ | ✓ | | |
| Pelvic floor muscle examination | ✓ | | ✓ | ✓ | ✓ | ✓ |
| surgical treatment | | ✓ | | | | |
| postoperative pathology | | ✓ | | | | |
| postoperative follow-up | | | | ✓ | ✓ | ✓ |

| | | | | | | |
|--|---|--|---|---|---|---|
| rectal examination | | | ✓ | ✓ | ✓ | ✓ |
| Pelvic floor surface electromyography assessment | ✓ | | ✓ | ✓ | ✓ | ✓ |
| Functioning, quality of life questionnaire | ✓ | | | ✓ | ✓ | ✓ |

Schedule 1

LARS Bowel Function Questionnaire

Does the patient complain of abnormal bowel movements: Yes No
Patient complained of abnormal defecation as: increased frequency incontinence painful defecation inability to distinguish between gas and faeces other

Whether the patient is satisfied with the current state of defecation:
Satisfied Unsatisfied

Does the patient think that the current state of defecation affects daily life:

No effect Yes effect

Use of medication to improve bowel movements: Yes Name _____ No

Prophylactic fistula Yes No

Prophylactic Fistula Payback Time is time Year Month Day
No

1. Have you ever had uncontrollable flatulence (farting)?

| | |
|--------------------------------|---|
|  Never | 0 |
| points | |
| Yes, less than 1 time per week | 4 |
| points | |
| Yes, at least once a week | 7 |
| points | |

2. Have you ever had an accidental leakage of loose stool?

| | |
|--------------------------------|---|
|  Never | 0 |
| points | |
| Yes, less than 1 time per week | 3 |
| points | |
| Yes, at least once a week | 3 |
| points | |

3. How many times a day do you have a bowel movement?

| | |
|---|---|
|  More than 7 times per day (24 hours) | 4 |
| points | |
|  4~7 times per day (24 hours) | 2 |
| points | |
|  1~3 times per day (24 hours) | 0 |
| points | |
|  Less than 1 time per day (24 hours) | 5 |

points

4. Have you ever had to have another bowel movement within an hour of having one?

Never

0

points

Yes, less than 1 time per week

9 points

Yes, at least once a week

11

points

5. Have you ever had to flush to the loo because of an urgent bowel movement?

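### The 1-month electromyography endpoint gets only an unadjusted test, although a pre-treatment value is scheduled for every patient, and the starting point for pelvic floor recovery is not named

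*Combined protocol and SAP*

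**What the plan says.** **Endpoint.** Section IV(ii)2 lists "Glazer pelvic floor muscle surface electromyography, and quality of life scores after 1 month of stoma return". This is a single time point, and the text names no EMG variable.

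**Measurement.** Section V(iii) schedules tests of pelvic floor muscle function at five visits: before radical surgery, before closure, and 1, 3 and 6 months after closure. Their purpose is "to compare the recovery of pelvic floor muscle function". No starting point, end visit or summary measure is given. V(iii) does not mention EMG, but the schedule of visits has a row "Pelvic floor surface electromyography assessment" ticked at the same five visits. A separate row for pelvic floor muscle examination is ticked at those visits too.

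**Treatment timing.** Section V(i): "Starting from 1 month after radical rectal surgery, the infusion is performed once a week for 2 months". Section V(ii): "Stoma closure was performed 3 months after surgery", and "All patients were reviewed in an outpatient clinic at least 7 days before preparation for stoma closure".

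**Analysis.** The repeated-measures paragraph in Section X(ii)2 covers three instruments: "Secondary outcome indicators Wexner score, MSKCC Bowel Function Questionnaire, and QLQ-C30 Quality of Life Scale scores were analysed for repeated-measures data". EMG is not among them. What is left is the general rule in X(ii)1: a t-test, or a rank-sum test where its assumptions fail. That rule mentions neither a baseline nor a change score. Section VII does not list EMG among the follow-up indicators.

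**The concern.** Two things are left open for a named secondary endpoint in a trial of 60 patients.

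First, the rule that applies by default compares the arms without the one EMG value taken before any infusion, although the schedule collects it from everyone. If that value predicts the 1-month value, the precision it offers is lost.

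Second, recovery has no defined starting point, and two of the five visits precede closure. One, before radical surgery, is a true pre-treatment value. The other, before closure, comes after most or all of the infusions and can itself carry a treatment effect. An analyst who reads recovery as recovery after closure could reasonably start from it and so subtract part of the effect under study. With the choice unwritten, it could be made after the data are seen.

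**Working it through.** **Timing.** Infusions run from month 1 to month 1 + 2 = 3 after radical surgery, and closure is at month 3. The pre-closure test is therefore at or near the end of the course. Its day is not fixed and the outpatient review is at least 7 days before preparation for closure, so a last infusion could follow the test. It is still a measurement taken under treatment. No EMG is scheduled between radical surgery and the first infusion, so the pre-radical-surgery value is the only pre-treatment one.

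**Inputs.** The plan states no figure for EMG. Its only computed figure is the sample size for the primary endpoint (Section IX), which reproduces with the unpooled two-proportion formula:

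(1.960 + 0.842)² × (0.14×0.86 + 0.47×0.53) / 0.33² = 26.6, so 27 per arm; 27 / 0.9 = 30 per arm, 60 in total.

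I take n = 27 evaluable per arm and two-sided 5% from there. The following are my assumptions: SD 1 at each visit, a true 1-month difference d = 0.5 SD (0.75 SD as a second case), and a correlation rho between visits of 0 to 0.7.

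**Formulas.** Power is from the non-central t distribution with 52 degrees of freedom and non-centrality (difference / SD) × √(n/2).
- Level at 1 month: difference d, SD 1.
- ANCOVA on the pre-radical-surgery value: difference d, SD √(1 − rho²).
- Change from the pre-closure value: difference d × (1 − f), SD √(2(1 − rho)), where f is the share of the 1-month effect already present before closure.

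For d = 0.5 the level test has non-centrality 0.5 × √13.5 = 1.84 against a critical value of 2.007, which gives 44% power.

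**Adjusting for the pre-radical-surgery value**

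| rho | Residual SD | ANCOVA, d = 0.5 | Unadjusted, d = 0.5 |
|---|---|---|---|
| 0 | 1.00 | 44% | 44% |
| 0.2 | 0.98 | 45% | 44% |
| 0.3 | 0.95 | 47% | 44% |
| 0.5 | 0.87 | 55% | 44% |
| 0.7 | 0.71 | 71% | 44% |

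Using 51 instead of 52 degrees of freedom for ANCOVA changes none of these at this rounding. At d = 0.75 the unadjusted test has 77% power, and ANCOVA has 81% to 97% for rho 0.3 to 0.7.

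**If the pre-closure value were the starting point (d = 0.5)**

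| f | Expected difference | Power at rho 0.3 / 0.5 / 0.7 |
|---|---|---|
| 0 | 0.50 SD | 33% / 44% / 64% |
| 0.5 | 0.25 SD | 12% / 15% / 21% |
| 1 | 0 | 5% (the type I error rate) |

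Using the pre-closure value as a covariate does not avoid the problem. The expected adjusted difference is then d × (1 − rho × f); for example, 0.5 × (1 − 0.5 × 0.5) = 0.375 SD at rho = f = 0.5.

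**The case against.** A reader might infer that Sections IV and V(iii) contradict each other, one asking for a level and the other for a change. The documents do not support that. Measuring at more visits than the endpoint visit is ordinary practice; the questionnaires are handled the same way, with a 1-month endpoint in Section IV and four collection times in Section VI. Recovery in V(iii) is a statement of purpose, not a defined change score, and V(iii) does not itself name EMG.

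A reader might also infer that the plan will subtract out the treatment effect, or that two definitions in the plan would give opposite answers. No section plans a change from the pre-closure visit. The general rule applied to the 1-month value is a valid randomised comparison from which nothing is subtracted. The scenarios above show a reduced or absent difference, never a reversed one. The loss also depends on f, which is unknown: Section I places the hoped-for recovery after closure and says nothing about pelvic floor muscle, so f = 0 is plausible, and at rho 0.7 the change score would then beat the unadjusted level test (64% against 44%).

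Finally, the gain from ANCOVA may be small. The pre-radical-surgery test precedes the 1-month test by at least 4 months and two operations, so a low correlation is credible, and at 0.2 the gain is about one point.

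All of this stands, and it limits the point. It does not remove it: EMG still has no named variable or baseline, and adjustment loses essentially nothing even at zero correlation.

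**Conclusion.** The point holds as a minor improvement. For the 1-month EMG endpoint the plan falls back on a valid but unadjusted test and leaves unused a pre-treatment value that it already schedules. ANCOVA costs essentially nothing at correlation 0 and raises power from 44% to between 47% and 71% at correlations 0.3 to 0.7. These figures assume 27 per arm, equal SDs, a 0.5 SD difference and two-sided 5%; the documents give no SD, effect size or correlation for EMG.

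The unnamed starting point for recovery is a gap in specification, not an error in a planned analysis. It matters because the pre-closure value is post-randomisation and taken at or near the end of treatment. As a starting point it would remove the share f of the effect, from none to all. The primary endpoint, its test and the sample size are not affected.

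**What to change.** In Section X(ii)2, add a paragraph for EMG that:
- names the EMG variable to be analysed;
- compares its value 1 month after closure between arms by ANCOVA, with the pre-radical-surgery value as covariate;
- analyses months 3 and 6 with the same model, as supportive;
- reports the pre-closure value by arm as a post-treatment measurement, not to be used as baseline or covariate;
- states how a missing pre-surgery value is handled, for example by simple baseline imputation.

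In Section V(iii), refer to that paragraph for what is meant by recovery, and say whether the tests there include EMG.

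The cost is wording only, since every measurement is already scheduled. The analysis spends one degree of freedom and needs the missing-baseline rule.

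### Anastomotic fistula, severe stenosis and emergency surgery before closure are only exit reasons; no safety outcome is named, so a LARS benefit could be reported with no comparison of these harms

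*Combined protocol and SAP*

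**What the plan says.** **Exposure.** V(i) sets the schedule for the experimental arm: "Starting from 1 month after radical rectal surgery, the infusion is performed once a week for 2 months". Each session delivers 400-600 mL at about 100 mL/min. Controls get no special treatment. V(ii) adds: "Stoma closure was performed 3 months after surgery". The infusions therefore fall between month 1 and closure.

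**The events.** Item 2 of the exit criteria, III(iii), covers, after enrolment and before closure, "patients who required emergency surgery due to intestinal obstruction, perforation, or bleeding". Item 6 begins "Anastomotic fistula, severe anastomotic stenosis" and applies after radical rectal surgery.

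**Safety analysis.** X(i) 3 defines the set: "Cases that completed at least one safety evaluation data after enrolment constituted the safety population of this study". It continues: "The safety population was the primary population for the safety evaluation of this study". A safety evaluation is therefore intended, but its content is not given.

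**Other relevant text.**
- V(ii) schedules rectal palpation and lower gastrointestinal imaging before closure, to exclude leakage and stenosis.
- V(vi), on adverse events, covers patients who cannot perform the infusion and the handling of symptoms during it.
- The only surgical complication among the endpoints (IV) and observation indicators (VII) is intestinal obstruction after the closure operation.
- X(ii) 1 gives a general rule that categorical indicators are compared by chi-square.

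**The concern.** The infused segment contains an anastomosis that is one to three months old. If infusion damages it, the damage should appear as a fistula, a severe stenosis or an emergency operation before closure. Under III(iii) each of these leads to exit. A patient harmed in this way leaves before the 6-month LARS assessment, and no listed outcome records the event.

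A lower rate of major LARS has to be weighed against anastomotic harm. A report could follow the plan to the letter, present the LARS result, and say nothing about how these events divided between the arms. If follow-up stops at exit, later events in the same patients are lost as well.

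**Working it through.** **1. Where each event appears.**

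| Section | Fistula | Severe stenosis | Emergency surgery before closure |
|---|---|---|---|
| III(iii) Exit criteria | item 6 | item 6 | item 2 |
| IV Endpoints | no | no | no |
| V(ii) Pre-closure review | leakage checked to clear for surgery | checked to clear for surgery | no |
| V(vi) Adverse events | no | no | no |
| VII Observation indicators | no | no | no |
| X(ii) Named analyses | no | no | no |

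Obstruction after closure is counted, but it is a different event in a later period, when infusion has ended. The chi-square rule in X(ii) 1 applies to indicators. These events are not listed as indicators, and the rule gives no event definition, time window or denominator.

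**2. Patients per arm.** Inputs from IX: 14% against 47%, 80% power, two-sided 0.05, 10% dropout. With unpooled variance:

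n = (1.96 + 0.8416)² × (0.14×0.86 + 0.47×0.53) / 0.33² = 26.63, so 27 per arm.

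27 / 0.9 = 30 per arm, 60 in total. The plan's figure reproduces when 27 is read as per arm. I take 30 per arm below as an assumption, because the realised split may differ.

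**3. What 30 per arm can show about harm.** The exact (Clopper-Pearson) two-sided 95% upper limit for one arm with 0 events is

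1 − 0.025^(1/30) = 0.1157, or 11.6%.

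This bounds one arm's rate; it is not an interval for the difference between arms.

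**4. Why chi-square does not suit sparse counts.** Suppose 5/30 against 0/30. The expected number of events per arm is 5×30/60 = 2.5. Pearson chi-square without correction is 60×(5×30 − 0×25)² / (30×30×5×55) = 5.45, p = 0.020. Fisher's exact test on the same table gives p = 0.052. Against 0/30, Fisher's test needs 6/30 (p = 0.024) to fall below 0.05. The choice of test can decide the result.

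**5. Power, with assumed rates.** At 30 per arm, power is about 25% for 5% against 15%, 42% for 5% against 20%, and 19% for 10% against 20% (normal approximation). None of these rates comes from the documents. They show that the output should be an estimate with an interval, not a test.

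**The case against.** The strongest reply is that the counts are probably recoverable. The events must be recognised to apply items 2 and 6, the pre-closure review covers all patients, and nothing forbids a table of exits by reason and arm. This stands as a limit on the claim: the data need not be lost. What is missing is an obligation to count and compare them, and follow-up after exit.

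A second reply is that the Full Analysis Set keeps everyone given a randomisation number. That set is for efficacy. It neither names these harms nor says how they are reported.

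A third is that infusion starts at month 1, so earlier fistulas cannot be due to it. This is correct, and it is why the later window needs its own table.

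Three stronger readings are tempting, and the documents do not support them.
- A reader might infer that the trial announces a complication aim and then leaves it unmeasured. The introduction does mention reducing complications, but the formal Purpose (II) names only defecation complications, rectal function and quality of life, which the listed questionnaires largely address. The case rests on harm monitoring alone.
- A reader might infer that the sponsor intends no safety evaluation or means to hide these events. X(i) 3 shows that an evaluation is intended, and V(vi) gives stopping symptoms and has a doctor perform each patient's first infusion. Those rules protect the patient, but they do not say how events are counted.
- A reader might infer that infusion causes anastomotic harm. The documents contain no event data in either direction; the background even cites transanal irrigation as possibly protective.

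**Conclusion.** The point holds as an omission in the plan. The three events most plausibly linked to the intervention appear as exit reasons, no safety outcome is named, and entry to the Safety Set depends on an undefined evaluation. A LARS benefit could therefore be reported within the plan and without any comparison of these harms.

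The omission does not invalidate the test of major LARS, but a conclusion on benefit against harm needs these counts. It should be corrected.

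The amount of harm that could go unreported cannot be stated, because the documents give no event rates. The one useful scale figure is the 11.6% upper limit for 0/30, which assumes 30 per arm. The link between infusion and these events is a judgement from the site and timing of the infusion, not a finding.

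**What to change.** 1. Change exit items 2 and 6 so that, after randomisation, these events stop infusion but do not end follow-up.
2. Name anastomotic fistula, severe stenosis and emergency surgery before closure as safety outcomes, with event dates. State what counts as a safety evaluation.
3. Count the already scheduled pre-closure palpation and imaging result as a safety observation in both arms.
4. Report counts by arm in all randomised patients, with a risk difference and exact 95% CI in place of chi-square.
5. Show events from month 1 to closure in a supplementary table, among patients still in the study and event-free at month 1.

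**Cost.** Protocol and SAP wording, event dates, and continued follow-up of patients who stop infusion. The events and the pre-closure check are already part of the trial.

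**Downsides.** Intervals will be wide, so only large increases in harm could be excluded; the gain is disclosure and a bound, not power. If randomisation precedes month 1, the month-1 subset is selected after randomisation and should stand beside the all-randomised table, not replace it. Patients whose closure is delayed may lack the 6-month LARS score even if they stay in follow-up. Infused patients also have more contact with the doctor than controls, so events between visits may be detected unequally; counting the common pre-closure check reduces this only in part.
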